The relationship between RZL-012 injection and a potential increase in liver enzymes is not completely understood. In preclinical studies which were conducted by Raziel, a rise in AST enzyme levels was observed in the high doses female rat group (20 mg/rat (about 80 mg/kg), equivalent to a human dose >900 mg/subject), returning to normal levels within 14 days of recovery. Raziel Therapeutics continues to monitor closely for any changes in liver enzymes.

1.3.2. Benefits

The cytolytic effect of RZL-012 has been demonstrated in non-clinical in-vitro and in-vivo studies. When administered into subcutaneous tissue, this cytolytic effect translates into a reduction in subcutaneous tissue. The reduction in submental fat has been demonstrated in Phase 2a and Phase 2b studies. Confirmatory Phase 3 studies will be conducted.

3.0 STUDY OBJECTIVES AND ENDPOINTS

3.1 Study Objectives

3.1.1 Primary Objective

The primary objective of this study is to compare the pharmacokinetic profile of RZL-012 in subjects that are dosed in the submental fat (SMF) in a Chinese vs. a non-Chinese population.

3.1.2 Secondary Objectives

- To compare the efficacy of RZL-012 in SMF reduction measured on Day 84 versus baseline using the Clinician Assessment Tool (C-CAT) in Chinese vs. non Chinese population.
- To compare the efficacy of RZL-012 in SMF reduction measured on Day 84 versus baseline using the Subject Assessment Tool (S-CAT) in Chinese vs. non Chinese population.
- To determine the efficacy of RZL-012 in SMF reduction measured on Day 84 versus baseline using both Subject Self-Chin Assessment Tool (S-CAT) and the Clinician Assessment Tool (C-CAT) Chinese vs. non Chinese population;
- To compare the reduction in SMF on Day 84 versus baseline using the caliper measured submental thickness in a Chinese vs. non Chinese population
- To assess the safety of RZL-012 in the treatment of SMF reduction.

3.2 Study Endpoints

3.2.1 Primary Endpoint

The pharmacokinetic profile of RZL-012 will be compared in a Chinese vs. a non-Chinese population based on:

- C_{max} Maximum concentration achieved.
- T_{max} Time to reach maximum concentration (hours).
- AUC_{last} The area under the concentration vs. time curve, calculated as sum of AUCs using linear trapezoidal summation from time 0 to the last measurable data point.
- AUC_{partial} The area under the concentration vs. time curve, calculated as sum of AUCs using linear trapezoidal summation from time 0 to the maximal measurement (T_{max}).
- $\lambda_{z \text{ (Lambdaz)}}$ Individual estimate of the terminal elimination rate constant, was calculated using log-linear regression of the terminal portions of the plasma concentration-versus-time curves.
- AUC_{inf} The area under the plasma concentration-time curve extrapolated to infinity,

calculated as:

AUC_{last} + Clast/ λz , where C_{last} is the last measurable concentration.

• $T_{1/2}$ - Apparent terminal elimination half-life time (hours), defined as $0.693/\lambda z$.

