8.6 Pharmacokinetics

Blood samples for testing of RZL-012 pharmacokinetics will be taken from all subjects at the baseline visit prior to injection, at 30 and 60 minutes post dosing and at 2h, 3h, 4h, 6h, 8h, 24h, 30 and 48 hours post injection.

Each sample (10 mL each) will be collected in K₂EDTA vials which will be stored on an ice block or wet ice until centrifuged with 60 minutes of collection. Samples will be centrifuged at 1200 g in 4 °C for 10 minutes. Plasma will be removed and placed in aliquots (4 aliquots of 1 mL each) within 20 minutes of centrifugation and flash frozen on dry ice. Processed samples will be placed in frozen (-60 to -90 °C) storage. Levels of RZL-012 in K₂EDTA human plasma will be determined using a validated method of Liquid Chromatography-Tandem Mass Spectrometry. Two aliquots from each time point will be retained for possible future analysis from all subjects

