5. PROCEDURE

• Introduction

This Statistical Analysis Plan (SAP) is based on **RZL-012-SMFC-P2US-001** study protocol version 1.2, dated 26 July 2022.

This Statistical Analysis Plan (SAP) contains details of the statistical analyses that will be performed, providing a more detailed description of the approach defined in the study protocol. Definitions of variables and populations used for the analyses are also included. The SAP will be finalized and signed prior to hard lock of the database.

General output specifications are provided; examples are given of calculations of derived variables.

• Study Objectives and Endpoints

Primary Objective

To compare the pharmacokinetic profile of RZL-012 in subjects that are dosed in the submental fat (SMF) in a Chinese vs. a non-Chinese population.

Secondary Objectives:

- To compare the efficacy of RZL-012 in SMF reduction measured on Day 84 versus baseline using the Clinician Assessment Tool (C-CAT) in Chinese vs. non-Chinese population.
- To determine the efficacy of RZL-012 in SMF reduction measured on Day 84 versus baseline using both Subject Self-Chin Assessment Tool (S-CAT) and the Clinician Assessment Tool (C-CAT) in a Chinese vs. a non-Chinese population.
- 3. To compare the reduction in SMF on Day 84 versus baseline using the caliper measured submental thickness in a Chinese vs. a non-Chinese population
- 4. To assess the safety of RZL-012 in the treatment of SMF reduction.

Medi Stat	document number: 140-BST-PLN-001	page: 8 of 20
TITLE: Statistical Analysis Plan of Protocol Number RZL-012-SMFC-P2US-001		EFFECTIVE DATE: 03/08/2022 REVISION NUMBER: 1.0

Primary Endpoints:

Characterization of RZL-012 pharmacokinetic (PK) profile in a Chinese vs. non-Chinese population based on

- Cmax Maximum concentration achieved.
- T_{max} Time to reach maximum concentration (hours).
- AUC_{last} The area under the concentration vs. time curve, calculated as sum of AUCs using linear trapezoidal summation from time 0 to the last measurable data point.
- $AUC_{partial}$ The area under the concentration vs. time curve, calculated as sum of AUCs using linear trapezoidal summation from time 0 to the maximal measurement (T_{max}).
- λ_z (Lambda_z)- Individual estimate of the terminal elimination rate constant, will be calculated using log-linear regression of the terminal portions of the plasma concentration-versus-time curves.

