 - The characterization of RZL-012 pharmacokinetic (PK) profile and comparison in a Chinese vs. a non-Chinese population

The following parameters will be evaluated for RZL-012 injection treatment for every subject:

- C_{max}: Maximum measured plasma concentration over the time span specified.
- T_{max} : Time to maximum measured plasma concentration. If the maximum value is observed at more than one time point, T_{max} will be defined as the first time point observed with this value.
- AUC_{0-t}: The area under the plasma concentration versus time curve, from time 0 to the last measurable concentration, as calculated by the linear trapezoidal method.
- AUC_{0-inf}: The area under the plasma concentration versus time curve from time 0 to infinity. AUC_{0-inf} is calculated as the sum of AUC_{0-t} and the ratio of the last measurable plasma concentration to the elimination rate constant.
- $k_{el}(\lambda_z)$: Apparent first-order terminal elimination rate constant calculated from a semilog plot of the plasma concentration versus time curve. The parameter will be calculated by linear least-squares regression analysis using the maximum number of points in the terminal log-linear phase. (e.g., three or more non-zero plasma concentrations).
- T₂: Apparent first-order terminal elimination half-life will be calculated as 0.693/k_{el}.
- C_{last} / λ_z : C_{last} is the last measurable concentration.

Other pharmacokinetic parameters may be calculated if deemed necessary.

Medi Stat	document number: 140-BST-PLN-001	page: 16 of 20
TITLE: Statistical Analysis Plan	of Protocol Number RZL-012-SMFC-P2US-001	EFFECTIVE DATE: 03/08/2022 REVISION NUMBER: 1.0

A total of 10 subjects per group will be used to compare between PK profile of both populations.

PK assessments will be compared between the 2 study populations. The individual values of for RZL-012 plasma concentration and evaluated PK parameters will listed by subject.

Summary tables will be generated for RZL-012 concentration by time point and for all derived PK parameters presenting sample size (N), mean, Standard deviation, Standard Error, Median, minimum and maximum values, Coefficient of variation (CV%) and 95% CI (Confidence Interval) for means by study arm.

Graphical displays will be generated presenting mean concentration by study arm as well as individual graphs per subject.

• Analysis of Safety Endpoints (Exploratory)

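### AUCpartial, a primary PK parameter, stops at each subject's own observed Tmax, so it mixes concentration with window length and cannot be compared cleanly between the two populations

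*Protocol*

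**What the plan says.** - **Role.** Protocol 3.2.1 opens the primary endpoint with "The pharmacokinetic profile of RZL-012 will be compared in a Chinese vs. a non-Chinese population based on", followed by seven parameters: Cmax, Tmax, AUClast, AUCpartial, λz, AUCinf and T1/2.
- **Definition.** For AUCpartial, Protocol 3.2.1 specifies "linear trapezoidal summation from time 0 to the maximal measurement (T_{max"). The primary endpoint list in SAP section 5 has the same rule: "calculated as sum of AUCs using linear trapezoidal summation from time 0 to the maximal measurement", again with Tmax in brackets.
- **Level of derivation.** SAP section 6 introduces its PK list with "The following parameters will be evaluated for RZL-012 injection treatment for every subject". Tmax is on that list, so it is an individual value. No fixed hour or group-level Tmax is given anywhere as the upper limit.
- **Sampling.** Protocol 8.6 takes a pre-dose sample and then samples "at 30 and 60 minutes post dosing and at 2h, 3h, 4h, 6h, 8h, 24h, 30 and 48 hours post injection". Observed Tmax can only be one of these ten post-dose times.
- **Analysis.** SAP section 6 says "A total of 10 subjects per group will be used to compare between PK profile of both populations", with listings, summaries by arm and graphs. Its parameter list omits AUCpartial. The only sentence that could bring it in is "Other pharmacokinetic parameters may be calculated if deemed necessary".

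**The concern.** An area is comparable between subjects when it covers the same interval. Here the interval ends at the subject's own peak. The value therefore depends on how high the concentrations were and also on how long the window was, and the window moves in whole sampling steps, the largest early one being 8 h to 24 h.

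The populations may differ in absorption rate, which is one thing a bridging PK study would want to detect. If they do, the window differs systematically between arms. The arm with slower absorption and lower early concentrations can then show the larger AUCpartial. A difference in this primary parameter could not be read as a difference in exposure up to any stated time, and it could point the wrong way.

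**Working it through.** The plan states no figure on this point to reproduce. I tested the definition on the protocol's own sampling times.

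**Inputs from the documents.** Times 0, 0.5, 1, 2, 3, 4, 6, 8, 24, 30 and 48 h (Protocol 8.6); linear trapezoids from 0 to observed Tmax (Protocol 3.2.1, SAP 5); 10 subjects per arm (SAP 6).

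**Assumptions.** One compartment, first-order absorption, zero concentration pre-dose, same dose, clearance and volume: C(t) = ka/(ka − k) × (e^(−kt) − e^(−ka·t)), with k = ln 2 / half-life. Values are in units of dose/volume. The documents give no PK constants, so I varied ka and the half-life.

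**Case A: half-life 12 h, k = 0.0578/h.**
- ka = 3/h. C at 0.5, 1, 2 h = 0.763, 0.912, 0.906. Observed Tmax = 1 h. AUCpartial = 0.25 × 0.763 + 0.25 × (0.763 + 0.912) = 0.609 (unrounded inputs). AUC0-2h = 1.518.
- ka = 1/h. C at 0.5, 1, 2, 3, 4 h = 0.387, 0.611, 0.802, 0.840, 0.823. Observed Tmax = 3 h. AUCpartial = 0.25 × 0.387 + 0.25 × (0.387 + 0.611) + 0.5 × (0.611 + 0.802) + 0.5 × (0.802 + 0.840) = 1.874. AUC0-2h = 1.053.
- Slow against fast: Cmax 0.840/0.912 = 0.92 (down 8%); AUC0-2h 1.053/1.518 = 0.69 (down 31%); AUC0-4h 2.705/3.233 = 0.84 (down 16%); AUCpartial 1.874/0.609 = 3.1.

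**Case B: half-life 6 h, k = 0.1155/h.**
- ka = 2/h. C at 0.5, 1, 2 h = 0.611, 0.802, 0.823. Tmax = 2 h. AUCpartial = 0.25 × 0.611 + 0.25 × (0.611 + 0.802) + 0.5 × (0.802 + 0.823) = 1.319.
- ka = 1/h. C at 0.5, 1, 2 h = 0.381, 0.591, 0.744. Tmax is still 2 h. AUCpartial = 0.25 × 0.381 + 0.25 × (0.381 + 0.591) + 0.5 × (0.591 + 0.744) = 1.006, a fall of 24%.

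The measure is a sawtooth: it falls while Tmax stays on one sample and jumps when Tmax moves to the next. At half-life 6 h it goes 1.826, 1.041, 2.944 for ka 0.1, 0.05, 0.03/h, with Tmax at 8, 8 and 24 h. If the peak is the first sample, AUCpartial is one triangle, 0.5 × 0.5 × Cmax = 0.25 × Cmax, and adds nothing to Cmax.

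**Two arms of 10.** 1,000 simulated trials, 30% CV on ka and ke, 10% error per sample, true total exposure equal. Median geometric mean ratio, slow arm over fast arm:

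| ka fast → slow (/h), ke (/h) | AUC to own Tmax | AUC0-4h |
|---|---|---|
| 2 → 1, 0.1 | 1.41 | 0.87 |
| 1 → 0.5, 0.1 | 1.21 | 0.76 |
| 0.1 → 0.05, 0.5 | 0.74 | 0.54 |
| 1 → 1, 0.1 | 1.00 | 1.00 |

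The first two rows point the wrong way. The third, where absorption is rate-limiting, understates the fall. Without a true difference there is no bias.

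**Noise.** Identical true PK in every subject, lognormal error per sample, 20,000 replicates, half-life 6, 12 and 24 h, ka 0.7, 1 and 1.5/h:
- 15% error: CV of AUCpartial 39-55%; AUC0-4h about 7-8%; Cmax 10-11%.
- 5% error: CV of AUCpartial about 25-39%; AUC0-4h about 2.5%.

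Near a flat peak, error alone decides which sample is called Tmax.

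**The case against.** **Direction.** A reader might infer that AUCpartial always rises when absorption slows. The definition does not imply that. Case B shows a fall with absorption still much faster than elimination, and the rate-limited simulation shows a fall too. The tripling in Case A comes from one choice of constants that moves Tmax by two samples; at the same half-life, ka 2 to 1/h gives 1.385 to 1.874, a rise of 35%. What stands is that the direction is unpredictable.

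**Unique windows.** A reader might also infer a different window in every subject. With ten post-dose times and 20 subjects, some must share a Tmax. The window varies with Tmax; it is not unique to each subject.

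**Purpose.** Neither document calls AUCpartial a measure of early exposure; it is defined only as the area up to the peak. That is fair, and I do not hold it to that label. The plan does compare it between populations, and the difference then has no reading as exposure over a stated interval.

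**Consequence.** Cmax, AUClast and AUCinf are also primary and are not cut at Tmax, and Tmax is reported beside them and would help explain an odd AUCpartial. No PK margin or decision rule rests on AUCpartial, and the SAP's sample size section says p-values serve only to show trends. SAP section 6 takes precedence over the protocol on analysis and omits the parameter, so it may never be tabulated. Individual concentrations will be listed, so a fixed-window area could be computed later. All of this stands and limits the damage, but none of it repairs the definition: summaries by arm would carry the same distortion, and a window chosen after the data are seen would be open to selection.

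**Conclusion.** The point holds as a defect of definition with moderate impact. AUCpartial as written mixes concentration with a window that depends on Tmax. A difference between Chinese and non-Chinese subjects cannot be interpreted as a difference in exposure up to a given time and can have the wrong sign.

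The sizes rest on an assumed one-compartment model and assumed error of 5-15% per sample; the study's real constants could give smaller or larger effects. The dependence on Tmax does not rest on the model, since it follows from the definition and the sampling schedule.

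It would go too far to conclude that the primary PK comparison as a whole is invalid: the remaining primary parameters are not truncated at the peak.

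**What to change.** In Protocol 1.1 and 3.2.1 and in SAP section 5, define AUCpartial as the area from 0 to one scheduled sample time, the same for all 20 subjects and fixed before any concentration data are seen. The sponsor should choose the time from earlier PK data; 4 h is used above only as an example, and the documents give no basis for a particular hour. A cut-off taken from this study's own data, such as the median Tmax of one arm, would depend on the results and is better avoided.

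Add the redefined parameter to the SAP section 6 list; otherwise it stays outside the planned analysis. The own-Tmax version can be kept in the listings only.

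The cost is about one sentence in each place, with no new samples or assays. The downside is that the new value is not comparable with any earlier study that used the own-Tmax definition.

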3.2.2 Exploratory Endpoints

The secondary endpoints for the study are:

- Comparison of the proportion of subjects in each population who have at least a 1-grade improvement in the C-CAT on Day 84 versus baseline.
- Comparison of the proportion of subjects in each population who have at least a 1-grade improvement in the S-CAT on Day 84 versus baseline.
- Comparison of the proportion of subjects in each population who have at least a 1-grade improvement in both the C-CAT and S-CAT (Day 84 versus baseline).
- Comparison of the proportion of subjects in both populations who have at least a 2-grade improvement in both the C-CAT and S-CAT (Day 84 versus baseline).
- Comparison of the reduction in SMF thickness measured with caliper (Day 84 versus baseline) in a Chinese vs. a non-Chinese population
- Safety of RZL-012 in the treatment of SMF reduction.

3.2.3 Additional Exploratory Endpoints

- Physicians Global Assessment
- SMF improvement using the Global Aesthetic Improvement Scale (GAIS).
- Subject Global Self-Assessment
- SMF improvement using the Subject Global Assessment of Change Scale.
- SMF improvement using the subject's satisfaction questionnaires.
- SMF improvement using Subject's Impact Questionnaire.

4.0 STUDY DESIGN

4.1 Overall Design

This is a Phase 2, open-label study that will consist of a screening period, baseline period in which subjects will receive a single treatment session of RZL-012 and a follow-up period. The single treatment session will consist of multiple injections of RZL-012 into the submental area under the chin. Blood samples will be collected from all subjects for PK analyses in the first 48 hours after dosing. Subjects will thereafter be monitored for safety and efficacy for at least 84 days.

All subjects will be treated with a total dose of 270 mg RZL-012.

